Eligibility Criteria

Inclusion Criteria

- Infants, \leq 37 weeks gestation at birth
- Current care provided by the UAMS NICU
- Parents/LARs must be able to provide written consent

Exclusion Criteria

- Entering palliative care
- Known diagnosis of liver disease
- On isolation precautions
- Approaching end-of-life
- On minimal stimulation protocol
- Any other condition, that in the opinion of the investigator, might interfere with the safe conduct of the study or place the subject at increased risk

Study Design and Procedures

This study is a cross-sectional pilot study to characterize the response of neonatal premature skin to DRS when excited with a white light source, and provide a baseline of how the collected spectra change with the maturation of the epidermal layer in the weeks to term gestation after birth by using a correlation analysis. It will be conducted in the UAMS NICU. A device employing related technology, the Philip's BiliChek System, is currently used to assess the level of bilirubin in infants with proven accuracy. As such, BiliChek readings will be taken as an evidenced-based practice reference along with DRS spectra. Accordingly, DRS spectra and BiliChek readings will be performed on consented study subjects admitted to the NICU. The pilot data will be used to evaluate whether DRS spectra can be used to extract optical information (scattering coefficient) related to skin maturity as well as hemoglobin, melanin, and bilirubin concentrations (mg/mL). DRS spectra will be compared to a lookup table created from published absorbance spectra (collected with a spectrophotometer) for bilirubin, hemoglobin, and melanin, and converted into relative concentrations for each chromophore [5,6,7]. The DRS-derived bilirubin concentrations and BiliChek-derived bilirubin measurements will be compared with the primary criteria for success being a high, positive correlation ($r \geq 0.85$, Pearson's correlation coefficient).

The following coded data will also be collected only once during a 24-hour window before and/or after DRS readings as routine standard of care to investigate correlations with the DRS spectra: blood oxygen saturation, weight, race, ethnicity, corrected age, gestational age, sex, most recent

Title: Characterization of Preterm Neonatal Skin by Diffuse Reflectance Spectroscopy Pilot Study

Principal Investigator: [name], DNP, RNC-NIC

Sponsor: University of Arkansas for Medical Sciences (UAMS)

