Study procedures include 1 study episode in which DRS and BiliChek measurements will be collected on intact skin at 4 anatomical sites per subject. Readings (i.e., when the probe makes contact with the skin) will only be performed on intact skin while broken or excoriated skin will not be tested. Qualified medical personnel will conduct a visual observation to assess for intact skin per standard of care. The 5 BiliChek readings will be performed first at each of the 4 anatomical locations on the subject (chest, upper arm, outer thigh, and forehead) to produce a single BiliChek measurement at each anatomical location, followed by 5-10 DRS readings (each of which produces a DRS average measurement) at each of the 4 anatomical locations for a total of 4 BiliChek measurements and a total of 20-40 DRS measurements. The BiliChek measurements will be recorded on the subjects electronic medical record following established NICU protocol, to include documentation in the nurses note. The testing locations were chosen to provide a wide range of data without having to move the subject from the position during the handling time with a nurse. Prior to beginning testing, each engineer will review the BiliChek measurement process steps and will duplicate the same practice for DRS readings with the PI or Sub-I to confirm aseptic techniques are followed. Spectra will be initiated within 10 minutes (+ 1 minute) of the completion of the final BiliChek reading. The cumulative light exposure that occurs over those 5-10 readings at each given anatomical location will not exceed 1 minute since the time to collect each individual reading is 0.1-0.2 seconds. Approximately 15 seconds (\pm 5 seconds) is needed between each anatomical location to allow for repositioning of the DRS probe and following unit guidelines for device use and cleaning. After all the data acquisition has been collected for the subject, the DRS probe and the BiliChek device will be wiped down with germicidal disposable cloths, as per unit cleaning protocol.

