Title: Characterization of Preterm Neonatal Skin by Diffuse Reflectance Spectroscopy Pilot Study

Principal Investigator: [name], DNP, RNC-NIC

Sponsor: University of Arkansas for Medical Sciences (UAMS)

Protocol Deviation: any unintentional change, divergence, or departure from the study design or procedures defined in the protocol. Protocol deviations will be tracked and compiled in a Protocol Deviation Log. Deviations that potentially cause concern for the subject's health, safety, or rights will be reported to the Sponsor as soon as possible for guidance on reporting.

Protocol Violation: a change to, or non-compliance with, the IRB-approved procedures without prior Sponsor and IRB approval (excluding changes made to eliminate apparent immediate hazard to subjects). A violation may affect health, safety, or rights of a subject. Any violation will be reported immediately to the Sponsor for guidance on reporting.

If the protocol deviation/protocol violation does not represent a significant alteration in the approved protocol and/or affect the safety or welfare of the subject, it will be reported to the UAMS IRB at the time of Continuing Review. If the protocol deviation/violation represents a significant alteration in the approved protocol and/or if it affects the safety or welfare of the subject, it must be reported to the Sponsor and UAMS IRB immediately.

Study Discontinuation and Withdrawal

Subjects have the right to withdraw from the study at any time for any reason. The study will be stopped in the event of a sentinel clinical outcome to one or more subjects. A sentinel event is a subject safety event that results in death, permanent harm, or severe temporary harm. Sentinel events are debilitating to both subjects and health care providers involved in the event.

Being a pilot study, all collected data will be analyzed and no subjects will be considered withdrawn from the study due to incomplete data collection. Subjects who have at least 5 readings at each anatomical location with both the BiliChek and DRS devices are considered completers of the study. Incomplete subjects will not be replaced; however, enrollment will continue until data for 44 completed subjects has been collected.

Data Handling and Recordkeeping

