Previous work has shown that the BiliChek results were very highly correlated to total serum bilirubin levels ($r = 0.88$) [9]. An *a priori* power analysis was conducted to determine the number of subjects needed to detect a similar strong correlation between the DRS and BiliChek data ($\alpha = 0.05$, power = 0.8, $r_0 = 0.7$, $r_1 = 0.85$; G*Power3.1). In this study, $n = 44$ completed subjects (≤ 37 weeks gestation at birth) will be recruited with the goal of maximizing biological variability (gestational age, sex, race/ethnicity) and validating our DRS system during the fewest visits possible. Subjects who have at least 1 measurement with both the BiliChek and DRS systems at a single anatomical location are considered completers of the study. Measured DRS spectra will be analyzed using a lookup table created from published absorbance spectra for each chromophore (e.g. hemoglobin, melanin, bilirubin) and the relative concentrations of the chromophores will be extracted [4]. The primary criteria for success will be a high, positive correlation ($r \geq 0.85$, Pearson's correlation coefficient) between the extracted DRS bilirubin concentration (dependent variable) and BiliChek-derived concentration (independent variable). The concentrations will be compared to blood oxygen saturation, weight, complete blood count, chemistry levels, lipids, liver profile, and blood gas, as available, by linear regression. In summary, the spectral and concentration data elements will be compared using linear regression and assessed using Pearson's correlation coefficient.

Ethical Considerations

This study will be conducted in accordance with all applicable government regulations and UAMS research policies and procedures. This protocol/ICF and any amendments will be submitted and approved by the UAMS IRB to conduct the study. All protocol and ICF amendments must be submitted to ORRA prior to IRB review.

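### Success rests on Pearson's r ≥ 0.85 alone, which supports correlation with BiliChek but not the matching or validation that the plan's wording suggests

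*Combined protocol and SAP*

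**What the plan says.** - **Objective.** Primary Objectives asks for DRS and BiliChek bilirubin to be compared by linear regression and Pearson's correlation.
- **Success rule.** It appears twice, each time with r ≥ 0.85: in Study Design and Procedures ("with the primary criteria for success being a high, positive correlation") and in Data Analysis ("The primary criteria for success will be a high, positive correlation").
- **Regression.** DRS is the dependent variable and BiliChek the independent one. Slope and intercept have no target and no part in success. The plan contains no mean difference, limits of agreement, concordance coefficient or acceptable difference.
- **Stronger wording.** Data Analysis speaks of "validating our DRS system during the fewest visits possible". Study Population says that the way the spectral analysis accounts for gestational age, race and ethnicity can be validated by bilirubin levels that match BiliChek.
- **Scale.** Study Design and Procedures refers to "hemoglobin, melanin, and bilirubin concentrations (mg/mL", but its description of the lookup-table step calls the output relative. Data Analysis agrees with the latter: "relative concentrations of the chromophores will be extracted". No BiliChek unit is given.
- **Data per infant.** Procedure provides "for a total of 4 BiliChek measurements and a total of 20-40 DRS measurements". Study Discontinuation and Withdrawal counts as completers "Subjects who have at least 5 readings at each anatomical location with both the BiliChek and DRS devices", whereas Data Analysis accepts "at least 1 measurement with both the BiliChek and DRS systems at a single anatomical location". No rule turns these measurements into one pair of values per infant.

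**The concern.** Two devices can be strongly correlated and still give different numbers. If DRS read half of BiliChek throughout, or a fixed amount above it, r would be the same as for a device with no such error, and the success rule would be met just as easily. A reader told that the system was validated, or that its levels match BiliChek, would take this to mean that the values agree. The rule cannot show that.

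What is at stake is the conclusion drawn from the pilot, not its conduct. Dissemination of Data foresees presentations and publications, and loose wording in the protocol can carry over into them.

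**Working it through.** **1. The plan's own figure.** Inputs from Data Analysis: α = 0.05, power 0.80, r₀ = 0.70, r₁ = 0.85. By Fisher's z, n = ((z_α + z_power)/(atanh 0.85 − atanh 0.70))² + 3. With a one-sided α this is ((1.645 + 0.842)/(1.256 − 0.867))² + 3 = 43.89 (unrounded inputs), so n = 44 reproduces. Two-sided it is 54.91, so 55, which does not. The sidedness is not stated. Either way, the sample size concerns correlation only; nothing in it refers to agreement.

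**2. What r ignores.** For any constant a and any c > 0, corr(B, a + cD) = corr(B, D), where B is BiliChek and D is DRS. To show this in numbers, 44 pairs were simulated with an assumed BiliChek mean of 8 and SD of 3 (arbitrary units, not from the documents), and the same DRS values were then rescaled or shifted:

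| DRS output | r | Slope | Mean DRS − BiliChek | 95% limits of agreement |
|---|---|---|---|---|
| as drawn | 0.889 | 0.85 | −0.11 | −2.64 to 2.42 |
| halved | 0.889 | 0.42 | −3.96 | −7.33 to −0.58 |
| shifted by +5 | 0.889 | 0.85 | +4.89 | 2.36 to 7.42 |
| doubled | 0.889 | 1.69 | +7.59 | 1.48 to 13.69 |

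All four meet r ≥ 0.85. The sizes depend on the assumed mean and SD; the equality of r does not.

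**3. What the planned regression adds.** The expected slope of DRS on BiliChek is r × SD(DRS)/SD(BiliChek).
- Unbiased device with equal SDs and r = 0.85: slope 0.85. SE = √((1 − 0.85²)/42) = 0.0813, so the 95% CI is 0.85 ± 2.018 × 0.0813 = 0.69 to 1.01.
- Device with slope 0.50 and r = 0.85: SE = (0.50/0.85) × 0.0813 = 0.0478, so the 95% CI is 0.50 ± 2.018 × 0.0478 = 0.40 to 0.60.

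The regression would therefore expose a gross scale error. But an unbiased device is not expected to give a slope of 1, so the slope alone does not settle bias.

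**4. What agreement reporting would give at n = 44 (illustration only).** Assumptions: absolute DRS output in the same unit as BiliChek, one pair per infant, true r = 0.85, equal SDs, zero bias. All results are in between-infant SDs.
- SD of the differences = √(2(1 − 0.85)) = 0.548.
- 95% limits of agreement = ±1.96 × 0.548 = ±1.07.
- 95% CI half-width of the mean difference = 2.017 × 0.548/√44 = 0.167.
- 95% CI half-width of each limit = 2.017 × 0.548 × √(1/44 + 1.96²/(2 × 43)) = 0.287, or about 0.29.

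If DRS output is only relative, none of the figures in this step apply.

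**5. Which values enter r.** Suppose the difference between devices has an infant component with variance t² and an independent site component with variance s². The mean over k paired sites then has variance t² + s²/k. The site part is four times as large for an infant with one site as for an infant with four. Under the one-site completer rule, pooling mixes the two kinds of infant.

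**The case against.** The strongest reply is that the criterion fits the aim. This is a pilot that sets out to characterise skin, its primary objective only compares the devices, and both places that define success say plainly that it means correlation. The matching phrase sits in Study Population and concerns how the spectral analysis handles gestational age, race and ethnicity; the validating phrase sits in a sentence about recruitment goals. No passage claims that DRS can replace BiliChek or proposes clinical use of its bilirubin values. All of this stands, and it is why r ≥ 0.85 should stay.

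Three stronger readings are tempting, and the documents do not support them:
- *That a correlation criterion is wrong for this study.* It answers the stated primary objective.
- *That bias would go unseen.* Regression is planned and would show gross bias; it simply has no say in success.
- *That limits of agreement are a required omission.* Both method descriptions call DRS output relative, and mg/mL appears once. On a relative scale, agreement cannot be assessed without a calibration step.

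It is also fair to say that agreement could be computed later from the same pairs if units allow, so no data would be lost. What remains is that two phrases promise more than the rule can deliver, and that the values entering any DRS–BiliChek statistic, r included, are not defined.

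**Conclusion.** The point holds as a cheap improvement, not as a fatal flaw. Meeting r ≥ 0.85 would support correlation between DRS and BiliChek bilirubin; it would not support matching or validation. That follows from the algebra of r and needs no assumption.

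The size of disagreement compatible with success is less certain. The ±1.07 SD limits, each known to about ±0.29 SD, rest on absolute output, one pair per infant, true r = 0.85, equal SDs and zero bias. A reader might infer that 44 infants are too few to study agreement, or that limits of this width are unacceptable. The documents give neither an acceptable difference nor an SD, so neither inference can be drawn.

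The fit between n = 44 and an observed-r rule is a separate matter: if the true r is 0.85, the rule is met with probability of only about 0.50 (Fisher's z) to 0.53 (exact distribution).

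**What to change.** In all cases:
- Keep r ≥ 0.85 as the correlation criterion and describe it as correlation only.
- In Data Analysis, replace the validating phrase with *assessing the correlation of DRS with BiliChek*. In Study Population, refer to levels that *correlate with* BiliChek rather than match it. The present wording can stay only if an acceptable difference, chosen by the investigators, is stated before analysis and agreement is judged against it.
- Reconcile the two completer rules, and reconcile the DRS scale (mg/mL or relative). State the BiliChek unit.
- Define one value per device per infant for r and the regression: average DRS within each site, then average each device over the sites that have both devices. Report the number of paired sites, and repeat the analysis in infants with all four sites, because infants with fewer sites have noisier differences.

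Only if DRS output is absolute and both devices are in one unit: also report the mean DRS − BiliChek difference and the 95% limits of agreement, with 95% confidence intervals. Call them descriptive unless an acceptable difference was stated in advance. They would describe a mean over up to four sites, not a single-site reading.

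**Cost.** No extra infants or readings; a few lines of text and a little more analysis. The result may look less favourable than r alone.

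### The success rule is an observed r of at least 0.85, but the 80% power belongs to a test of 0.70 against 0.85; if the true r is 0.85, the chance of success is about 53%

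*Combined protocol and SAP*

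**What the plan says.** The sample size paragraph in Data Analysis states its purpose as follows: "An *a priori* power analysis was conducted to determine the number of subjects needed to detect a similar strong correlation between the DRS and BiliChek". The inputs are alpha 0.05 and "power = 0.8, $r_0 = 0.7$, $r_1 = 0.85$; G*Power3.1", and the result is 44 completed subjects. The paragraph does not say whether alpha is one-sided or two-sided.

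The same section then gives the decision rule: "The primary criteria for success will be a high, positive correlation", which it sets at a Pearson r of 0.85 or more. Study Design and Procedures repeats it, describing the comparison of the two devices "with the primary criteria for success being a high, positive correlation", with the same cut-off of 0.85.

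The value 0.70 appears only among the power inputs. No section says that a null correlation of 0.70 will be tested, and none gives a p-value or confidence-bound criterion. The primary objective and the closing sentence of Data Analysis name only linear regression and Pearson's r.

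**The concern.** The plan contains two rules. One was used to choose the sample size: reject a true correlation of 0.70 when the truth is 0.85. The other will decide the result: the observed r reaches 0.85. The stated alpha and power describe the first rule only.

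The second rule puts its threshold at the value assumed to be true. A sample correlation exceeds its own true value about half the time, and a larger sample does not change that. A DRS system that performs exactly as the design assumes would therefore miss the criterion nearly half the time, while the protocol implies a 20% risk. A failure read against the stated 80% power would be taken as evidence against the device when it is close to a coin flip.

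**Working it through.** **Inputs (Data Analysis):** r0 = 0.70, r1 = 0.85, alpha = 0.05, power = 0.80, n = 44, success if observed r ≥ 0.85. **Assumptions added here:** bivariate normality and one independent DRS–BiliChek pair per infant.

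**1. Reproduce the stated sample size (Fisher z).**

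- atanh(0.85) − atanh(0.70) = 1.2562 − 0.8673 = 0.3889.
- One-sided: n = ((1.645 + 0.842) / 0.3889)² + 3 = 43.9, so 44. This matches the plan.
- Two-sided: n = ((1.960 + 0.842) / 0.3889)² + 3 = 54.9, so 55. This does not match.

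The figure of 44 is therefore correct for a one-sided 5% test. From the exact distribution of r, that test has power 0.799 at n = 43 and 0.808 at n = 44. If alpha were two-sided, exact power at n = 44 would be 0.708, with critical r 0.828.

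**2. Find the observed r at which the powered test succeeds.**

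- Fisher z, one-sided: tanh(0.8673 + 1.645/√41) = tanh(1.1242) = 0.809.
- Exact distribution: 0.812.

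The 80% power therefore belongs to a threshold of about 0.81.

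**3. Evaluate the written rule, observed r ≥ 0.85, at n = 44.**

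By Fisher z without the small-sample bias term, the chance at a true r of 0.85 is exactly 0.50. Adding that term, 0.85/(2 × 43) = 0.0099, gives Φ(0.0099 × √41) = Φ(0.063) = 0.525. Numerical integration of the exact density gives 0.526, and 200,000 simulated samples gave 0.525. The exact values over a range of true correlations are:

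| True r | P(observed r ≥ 0.85), n = 44 |
|---|---|
| 0.70 | 0.0076 |
| 0.80 | 0.170 |
| 0.85 | 0.526 |
| 0.88 | 0.800 |
| 0.90 | 0.928 |

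**4. Compare the two rules at n = 44 (exact).**

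| | Powered test (one-sided) | Written rule |
|---|---|---|
| Observed r needed | 0.812 | 0.85 |
| Success if true r = 0.70 | 0.05 | 0.0076 |
| Success if true r = 0.85 | 0.808 | 0.526 |

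An observed r between 0.812 and 0.85 satisfies the powered test but fails the written rule. If the true r is 0.85, this happens with probability 0.808 − 0.526 = 0.282.

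**5. Check whether more data would help.** At a true r of 0.85 the chance of meeting the written rule is 0.519 with 80 pairs. It is 0.513 with 176 pairs, which is 44 infants × 4 sites treated as if independent. The shortfall comes from where the threshold sits, not from the sample size.

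**The case against.** The strongest reply is that nothing is miscalculated. The figure of 44 is right for the test that was powered, and the plan never says in so many words that it has 80% power to observe r ≥ 0.85. On this view 0.85 is a benchmark for a pilot study, no clinical care depends on it, and the estimate of r is the same under any rule. The written rule is also the stricter one. An observed r of 0.85 at n = 44 has a one-sided 95% lower bound of tanh(1.2562 − 1.645/√41) = 0.76, so any pass also excludes 0.70. Finally, the 53% depends on a true r of 0.85; at 0.88 the rule does have 80% power.

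Much of this is true, and it narrows the point. A pass is safe to interpret, so the damage is confined to failures, above all observed values between about 0.81 and 0.85. The 53% must be stated as conditional on a true r of 0.85. But that is the protocol's own design alternative. The 0.88 it cites is for BiliChek against serum bilirubin, not DRS against BiliChek. Having set an alpha, a power and a primary pass/fail criterion, the plan should give the properties of the rule it will apply. Being a pilot does not remove that need.

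The missing sidedness is a small matter, since the wording is directional and only the one-sided reading gives 44. It still needs to be written down.

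**Conclusion.** The concern holds. The sample size arithmetic is correct, but the 80% power and 5% alpha describe a test that the plan does not apply. Under the only rule it does state, the chance of success at the planned true correlation of 0.85 is about 53%. The chance of being labelled unsuccessful is therefore about 47%, where readers would expect 20%. The chance of passing at a true r of 0.70 is about 0.8%, not 5%. Power of 80% is reached only if the true r is 0.88.

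These figures assume bivariate normality and one independent pair per infant. The plan does not say how the four sites enter r, but the result stays near one half even if all 176 pairs are treated as independent.

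**What to change.** Make the rule and the power statement agree, by one of two routes.

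- **(a) Keep r ≥ 0.85 and restate its properties.** Say that with 44 infants the criterion is met with probability about 53% if the true r is 0.85, 80% if it is 0.88, and 0.8% if it is 0.70. The success criterion does not change; the cost is a less favourable power figure.
- **(b) Adopt the test that was powered.** Define success as the one-sided 95% lower confidence bound for r exceeding 0.70, which at n = 44 means an observed r of about 0.81 or more, and report 0.85 as a descriptive benchmark. This lowers the observed threshold for the primary criterion, and the plan should say so openly. It also requires the analysis unit to be fixed at one pair per infant, because the critical r moves with the number of pairs: by Fisher z it is about 0.78 at 80 pairs and 0.76 at 176.

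Under either route, state that alpha is one-sided and report r with its confidence interval. Make the choice before the DRS–BiliChek correlation is examined; a threshold moved afterwards would not be credible.

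Neither route changes enrolment or procedures. The cost is a wording amendment, which under Ethical Considerations goes to ORRA and then the IRB.
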